Cold Pressor Testing and CPM: A series of procedures designed to elicit and measure endogenous inhibition of pain will be applied. Subjects will undergo a series of cold pressor tasks (i.e., the conditioning stimuli) consisting of immersion of the hand in a circulating cold water bath. During hand immersion, pressure responses or temporal summation will be re-assessed while subjects' hands remain in the cold water. Subjects may remove their hand at any time. Two minutes after finishing the first immersion, subjects will re-immerse their hand in the water, and one of these tests (pressure response or temporal summation) will be re-assessed, each separated by 2 min (the tests will be conducted in random order). A CPM Index is quantified as the average percent change (across trials) in PPT_h or TS during the cold pressor tasks relative to baseline ratings¹¹⁹. One final cold-water immersion will be performed at the conclusion of the CPM procedures. This will involve a typical cold pressor task, using immersion of the hand until the subject's tolerance is reached, with a 5-minute uninformed time limit.

CS: Temporal summation measures, CPM, and after-sensation responses to these measurements will be combined to create the CS index for use in statistical analyses for which we have previously published⁵⁷. Physical Performance Measures will objectively assess physical functioning. Patient self-report of activity relates only modestly to performance measures on standardized physical tests¹²⁰⁻¹²⁵ and physical performance under the effects of the drugs administered here are an essential test of the real-world applicability of administering such analgesic combinations in the natural environment. This set of tests will involve a Timed Up and Go (TUG) test. Stair climb (which includes hand rails) and a three-Minute Walk (3MW) test, all commonly used measures of KOA physical function¹²⁶. The TUG test measures the time it takes a subject to rise from a standard chair, walk 3m, and then return to sitting in the same chair. In the 3MW test, subjects are asked to cover as much distance as possible in 3 minutes while walking laps on a standardized indoor course. Each test will be conducted at baseline and at projected peak effect to avoid participant fatigue.

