a. Primary outcome variable:

Aim 1: Evaluate the magnitude and duration of cannabinoid/opioid combination to reduce clinical pain (Hyp1) and central sensitization (Hyp2). Hyp1 (pain VAS) and Hyp 2 (CS) will be analyzed using repeated 2-factor (Drug x Time) models that examine linear and quadratic effects as well as duration and magnitude, and direct and interaction effects. If large variation exists across subjects at baseline, then raw data will be transformed to change-from-baseline and analyzed in drug condition by time models. A secondary outcome will be peak change from baseline, analyzed as a function of Drug (1-factor model).

- Aim 2: Evaluate the degree to which physical functioning is altered by the cannabinoid/opioid combination.** Hyp3 will be assessed using the TUG and 6MWT. Time to complete the TUG task will be the primary outcome and will be evaluated using 2-factor (Drug x Time: Pre to Peak) models.
- Aim 3: Conduct a direct comparison of the subjective, physiological, abuse liability, and cognitive effects of the cannabinoid, opioid, and combination.** Hyp4 (adverse events) will be assessed by summing the mean number of related mild, moderate, and severe adverse events (separately) and using 1 factor models to assess a main effect of Drug. Hyp5 (abuse liability) will be assessed using the Drug vs. Money questionnaire and changes in VAS ratings using 2-factor models (Drug x Time). Hyp6 will evaluate changes in neurocognitive performance, including study session number as a covariate to control for practice effects, using 2-factor (Drug x Time) analyses. Secondary outcomes for this hypothesis will be analysis of peak change from baseline for the cognitive outcomes, analyzed using 1-factor (Drug) ANOVAs to evaluate a main effect of drug.

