- Aim 4: Evaluate the pharmacokinetic (pK) and pharmacodynamic (pD) profile of the cannabinoid, opioid, and the combination in OA patients.** Hyp 7 (pK) will be assessed by evaluating Cmax (maximum concentration) and Tmax (time to maximum concentration) as a function of Drug condition using 1-factor models. We will also examine linear and quadratic effects to evaluate the time course of concentration. Linear and quadratic effects will be modeled for Hyp8 (pD) and analyzed by evaluating VAS and physiological ratings, transformed to change from baseline, evaluating area under the curve and peak change from baseline to identify main effects of the Drug condition. We will then conduct multivariate regression analyses to evaluate the degree to which the Cmax and Tmax correlate with pharmacodynamic outcomes, including abuse liability ratings, VAS ratings of drug effects, and cognitive testing outcomes.

Statistical analyses will be conducted separately by Phase and use multilevel analyses with an autoregressive (AR1) or compound symmetry (CS) covariance structures (as appropriate for the data set) using SAS PROC MIXED¹³⁷. Interpretation of drug condition main effects and interactions will rely on Tukey post-hoc tests. Statistical significance will be set at $p < 0.05$.

Expected Outcomes: We expect that dronabinol will enhance hydromorphone-induced analgesia to both clinical and laboratory-evoked pain. Our comprehensive battery of rigorous, testing procedures provides an opportunity to test effects on multiple mechanisms of experimentally-induced pain. We also expect improvement in physical functioning under combined dosing, and that the addition of the cannabinoid will not significantly increase the overall abuse liability or adverse event profile. We do suspect the cannabinoid may have cognitive effects (though the degree to which this may happen is not clear).

b. Secondary outcome variables.

Demographic and drug use characteristics that are hypothesized a priori to be associated with outcomes (e.g., Body Mass Index) will be compared across sex groups and significant differences will be included as covariates in the subsequent analyses. All analyses will be repeated and sex (male/female) will be added as a factor to the analyses.

c. Statistical plan including sample size justification and interim data analysis.

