This will be the first study to examine interactions between cannabinoids and opioids on clinical and laboratory-evoked measures of pain in a population who has chronic pain and central sensitization. The study uses a within-subject, placebo-controlled design and no data exist upon which to generate a power analysis. We have selected two primary outcomes for the measurement of analgesia: measures of conditioned pain modulation and time to hand withdraw latency in a cold presser test.

[name], a biostatistician with extensive experience analyzing within-subject laboratory tests of drug effects, conducted a revised power calculation based on new literature that employs methods similar to those of this study (Cooper et al., 2018). Sample size estimates were premised with a power of 0.8, alpha =0.05 and calculated effect sizes (Cohen, 1988). These analyses suggests a sample size ranging from 10-15 individuals would be sufficient to detect large effect sizes. Because one of our aims focuses on a sex-comparison, we originally planned to double our enrollment. Thus, our sample of 64 completers (32/sex) will yield sufficient power to evaluate direct effects of study condition on CPM and cold presser in both Phases, even at small effect size levels, and will also be sufficient to identify between-session differences on pK results¹⁴⁰.

d. Early stopping rules.

The safety of participants is the highest priority. The largest potential risk of this study is cardiovascular in nature. This notion is based upon the results of a published study that reported an increase in heart rate and blood pressure among patients exposed to the cannabinoid dronabinol who were also undergoing opioid withdrawal (of which increased heart rate and blood pressure is a known symptom). This group differs from our target population in many ways, however out of an abundance of caution in these early studies, we will use this experience to inform our safety criteria. We will monitor vital signs at all study data collection time points and will follow procedures that we have developed and successfully used in previous studies that administered drugs (e.g., cocaine) with known cardiovascular risks. Specifically, if a participant's parameters reach these thresholds, then a study physician, who will always be available via telephone, will be contacted and consulted to determine the appropriate course of action.

- Systolic blood pressure: $\geq 180\text{mm Hg}$

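### Sections 7.a and 7.c name different primary analgesia outcomes, and the explicit power claim covers only the 7.c list (plus pharmacokinetics)

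*Combined protocol and SAP*

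**What the plan says.** Section 7.a is headed as the primary outcome variable. For Aim 1 it states: "Hyp1 (pain VAS) and Hyp 2 (CS) will be analyzed using repeated 2-factor (Drug x Time) models". The only Aim 1 outcome it labels secondary is peak change from baseline. It closes with general rules for all analyses: "Statistical analyses will be conducted separately by Phase", and "Interpretation of drug condition main effects and interactions will rely on Tukey post-hoc tests".

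Section 7.c gives a different list: "two primary outcomes for the measurement of analgesia: measures of conditioned pain modulation and time to hand withdraw latency in a cold presser test". It then says that 64 completers, 32 of each sex, "will yield sufficient power to evaluate direct effects of study condition on CPM and cold presser in both Phases", and adds that this number also suffices for between-session pharmacokinetic differences. The preceding estimate of 10 to 15 participants for large effects names no outcome.

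Two paragraphs of Section 4.a (Measures) show how the quantities relate. On the index: "Temporal summation measures, CPM, and after-sensation responses to these measurements will be combined to create the CS index". On the cold pressor: "One final cold-water immersion will be performed at the conclusion of the CPM procedures"; that immersion is the one continued to tolerance.

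The Abstract, Section 2 (Aim 1) and the Study Design Overview in Section 4.a name domains rather than measures: clinical pain and central sensitization.

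**The concern.** Which result is primary is the first thing a prespecified plan has to settle, and here two sections settle it differently. If the pairs disagree (say, CPM and cold-pressor latency favour the combination while VAS and the CS index do not, or the reverse), the investigators could report either pair as planned and a reader could not object from the document. The choice could then be made after the data are seen.

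The second consequence is a mismatch between hypotheses and power. Hyp1 and Hyp2 are tested on pain VAS and the CS index, but the explicit power claim refers to other quantities.

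**Working it through.** **The two lists side by side**

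| Outcome | Section 7.a | Section 7.c |
|---|---|---|
| Pain VAS | Hyp1, Drug x Time model | not mentioned |
| CS index | Hyp2, Drug x Time model | not mentioned as an index |
| CPM alone | no hypothesis or named model | primary, power claimed |
| Cold-pressor withdrawal latency | no hypothesis or named model | primary, power claimed |

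The index combines temporal summation, CPM and after-sensations, so CPM is a component of the Hyp2 outcome. A component can give a different result from its composite. In the CPM procedure the cold water is the conditioning stimulus, and the index is the percent change in pressure threshold or temporal summation. Cold-pressor tolerance comes from a later, separate immersion and is not listed in the CS index.

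**The plan's own figure (10 to 15 participants).** Section 7.c gives power 0.8 and alpha 0.05, but no numeric effect size, SD, within-subject correlation, sidedness or test, so the figure cannot be reproduced from stated inputs. Under assumed inputs:
- Paired t-test, two-sided, noncentrality d x sqrt(n): d = 0.8 gives n = 15; d = 1.0 gives n = 10.
- Four-condition repeated-measures ANOVA, noncentrality n x 4 x f^2 / (1 - rho), f = 0.4: n = 10 at rho = 0.5 and n = 14 at rho = 0.3.

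The figure is therefore plausible for a generic large within-subject effect. It is not tied to either list.

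**What a restated power sentence could say (illustration).**
- Number per Phase: 7.a analyses each Phase separately. The Design Overview splits participants equally between the Phases, so 64 completers are assumed to give 64 / 2 = 32. Reading 64 as a per-Phase number would need 2 x 64 = 128 completers, more than the 100 to be studied. The ceiling with no dropout is 100 / 2 = 50.
- Assumptions: one summary value per condition, all four conditions completed, compound symmetry, two-sided tests.
- Effect: dz = mean paired difference / SD of the paired differences, with noncentrality dz x sqrt(n).
- Single unadjusted contrast at 0.05, df n - 1, 80% power: dz = 0.511 (n = 32) and 0.404 (n = 50).
- Tukey over four conditions, critical value = studentized range quantile / sqrt(2), df 3(n - 1). For n = 32: df 93, critical value 2.616, dz = 0.613 (check: 0.613 x sqrt(32) = 3.47). For n = 50: df 147, critical value 2.599, dz = 0.487.
- Hyp1 and Hyp2 need the combination to beat hydromorphone alone, dronabinol alone and placebo, which is three contrasts. In simulation with n = 32 and the same true dz for all three, dz = 0.613 gives about 62% power to win all three under Tukey. About 0.70 is needed for 80%.

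On this standardised scale the figures would be the same for any choice of outcomes. They show what the sentence should contain; they do not measure the inconsistency.

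**The case against.** **A benign reading of 7.c.** It might be adding laboratory measures of analgesia to the clinical ones in 7.a. But Aim 1 in Section 2 uses analgesia for both clinical pain report (Hyp1) and central sensitization (Hyp2), so a closed list of two primary analgesia outcomes competes directly with 7.a.

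**CPM as a marker of central sensitization.** Section 3 does call CPM a CS-specific task, and CPM fits the domain wording elsewhere. That narrows the gap for one of the two 7.c outcomes. It does not make CPM alone the same endpoint as the index, and it does nothing for cold-pressor latency or pain VAS.

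**The domain statements settle it.** The Abstract, Section 2 and the Design Overview fit 7.a better, but they do not withdraw the explicit primary label in 7.c. The misfit also runs both ways: pain VAS is as absent from 7.c as cold-pressor latency is from 7.a.

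**Cold-pressor latency is not without any analysis.** This stands in part. The general mixed-model paragraph in 7.a is not limited to named outcomes, so a default model could be applied. What is missing is a hypothesis and a named analysis.

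**This is a proof-of-concept laboratory study.** True, but an undetermined primary list remains a prespecification gap, and closing it is cheap.

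**Stronger readings to avoid.** A reader might infer that pain VAS or the CS index is underpowered, or that the sample size must change. The documents do not support either: they give no effect size or SD for these outcomes, and renaming the primary outcomes does not alter N on a standardised scale. Nor do they show that one list is the intended one and the other a slip.

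**Conclusion.** The plan is wrong as written on this point: two current sections conflict on which analgesia outcomes are primary, and no other text resolves it. The finding is textual and depends on no calculation. Its extent is two lists of two outcomes whose only link is that CPM is a component of the CS index, with the explicit power claim attached only to the 7.c pair (plus pharmacokinetics). Confidence is high.

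The detectable effects are illustrative. They rest on an equal 32/32 split of completers, which the document does not state, on compound symmetry (7.a also allows AR(1)), and on one summary value per condition where 7.a plans Drug x Time models. The three-contrast figure also assumes equal effects against all three comparators.

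**What to change.** Before unblinding:

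1. Put one primary analgesia list in both 7.a and 7.c. The simplest choice is pain VAS (Hyp1) and the CS index (Hyp2), which already have hypotheses and models and match the domains named elsewhere; stand-alone CPM and cold-pressor latency then become secondary. The alternative is to amend 7.a so that CPM and cold-pressor latency have hypotheses and models.
2. Restate the 7.c power sentence for that same list, at the planned number of completers per Phase. Name the summary measure (for example session mean, peak or area under the curve), the covariance assumption, and the contrasts, including whether power is for one contrast or for the combination beating all three comparators.

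The cost is text in two sections and one recalculation. No new data are needed, and no outcome SDs if the effect is stated in standardised units. The first option leaves the 7.a models and N unchanged, but the investigators must demote two outcomes they now call primary, which is a substantive decision. The alternative adds analyses.

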Study Design Overview: We propose to study the separate and combined effects of the FDA-approved cannabinoid dronabinol (Marinol) and the prototypical opioid hydromorphone (Dilaudid). Following telephone and screening to establish study eligibility, a cohort of **n=100** adults with knee osteoarthritis (KOA) will complete four different within-subject experimental sessions. Participants will complete one of two Phases, receiving either a 4mg or 2mg dose of hydromorphone. Randomization will be split equally across the two Phases. During each session, participants will complete baseline QST, questionnaires, and a neurocognitive battery. Oral hydromorphone will be administered in the first session. Subsequent sessions will consist of 1 of 3 conditions, and session order will be randomized and counter-balanced. Conditions will be 1) placebo; 2) oral dronabinol (10mg); and 3) combined hydromorphone and dronabinol (10mg). Measures will be repeated throughout the session to fully characterize the drug effects. Participants and staff will be kept blinded to the study medications under investigation, and participants will be informed in the consent form they may receive a combination of FDA-approved stimulants, benzodiazepines, opioids, cannabinoids, over-the-counter medications or placebo, though the participants will not actually be receiving stimulants, benzodiazepines, or over-the-counter drugs. All participants will be provided with transportation to and from the experimental sessions. Primary outcomes are measures of clinical pain, central sensitization, physical function and drug effects/adverse events. A subset of participants will undergo blood draws for pharmacokinetic (pK) profile. This will be voluntary and should aid recruitment as those that do not want an IV will still be allowed to participate in the study. We will aim to recruit 30 participants that volunteer to undergo IV/blood drawing procedures in order to characterize pK.

Phase 1: The initial Phase of this project will include hydromorphone at a dose of 4mg.

Phase 2: The second Phase of this project will include hydromorphone at a dose of 2mg in order to evaluate drug effects at a reduced opioid dose.

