Pain Testing: Subjects will complete quantitative sensory testing (QST) to comprehensively and systematically measure general pain sensitivity and central sensitization. This approach will provide data regarding the full range of analgesic effects possible, across a wide variety of psycho-physiologically-mediated, experimentally-induced measures of pain perception. Subjects will complete a baseline QST session prior to study drug administration on each experimental session day and the pain testing battery will be repeated approximately every 90 mins. The QST battery consists of threshold and tolerance, and temporal summation, and conditioned pain modulation (CPM) tests. The threshold responses will be conducted in randomized and counter-balanced order, and conditioned pain modulation will always occur last.

Threshold Responses will be assessed using thermal and pressure stimulation. *Thermal threshold:* All contact heat stimuli will be delivered using a peltier-element-based stimulator (Medoc, Israel). Two trials of heat pain threshold will be administered using a thermode that gradually increases in temperature from a pre-set baseline (31°C) until the subject indicates when the stimulus “first feels painful” (threshold, HPTh) and presses a button (which terminates the procedure) indicating that the pain is intolerable (tolerance, HPTo). *Pressure threshold:* Pressure pain thresholds (PPTh) will be determined at each of the following sites on both sides of the body using a pressure algometer (SBmedic; Sweden): the medial fat pad of the knee, patella, trapezius, and thumb. Pressure at the site is gradually increased at a steady rate and stopped when the subject indicates the stimulus is first perceived as painful. Thirty-second inter-stimulus intervals will be maintained. Trials will be averaged for one HPTh, HPTo, and PPTh measure.

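### Section 7.c claims adequate power for small effects in both Phases; under conventions that match its own figures, small-effect power is about 17–23% per Phase

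*Combined protocol and SAP*

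**What the plan says.** Section 7.c sets the premises: "Sample size estimates were premised with a power of 0.8, alpha =0.05 and calculated effect sizes". From these it concludes that "a sample size ranging from 10-15 individuals would be sufficient to detect large effect sizes". It then says that doubling enrolment for a sex comparison leads to 64 completers (32 per sex), and that this number gives "sufficient power to evaluate direct effects of study condition on CPM and cold presser in both Phases, even at small effect size levels". The same sentence extends the claim to between-session pharmacokinetic differences. No calculation for a small effect is shown, and no numeric effect size, within-person correlation or sidedness is given.

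Two other places fix how many people enter each analysis. The Study Design Overview in Section 4.a enrols 100 people and says "Participants will complete one of two Phases" and "Randomization will be split equally across the two Phases". Section 7.a says "Statistical analyses will be conducted separately by Phase". The Overview also limits blood sampling to a volunteer subset with a target of 30.

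**The concern.** Two things do not fit together. First, the 64 completers are spread over two Phases that are never analysed together, so neither analysis has 64 people. Second, Cohen's small effect is one quarter of his large effect (0.2 against 0.8, or 0.10 against 0.40). Required sample size grows with the inverse square of the effect, so a design that needs 10–15 people for a large effect needs roughly 16 times as many for a small one.

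Apart from the 10–15 for large effects, this sentence is all the plan says about what its sample can detect. The results are meant to inform whether the drug combination goes forward to clinical trials. A reader who trusts the sentence would take a null result in either Phase as evidence against even a small effect.

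**Working it through.** **Inputs from the plan.** Power 0.8, alpha 0.05, 10–15 for a large effect, 64 completers (7.c); four within-person conditions, 100 enrolled, one Phase per person, equal split (4.a); separate analysis by Phase and Tukey post-hoc tests (7.a).

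**Assumptions.** Two-sided testing. Cohen's benchmarks: paired standardised difference dz = 0.2, 0.5, 0.8, or ANOVA f = 0.10, 0.25, 0.40, for small, medium and large. Correlation rho between conditions 0.3–0.5. Completers per Phase are not stated: an equal split gives 64/2 = 32, and the most favourable reading (everyone enrolled completes) gives 100/2 = 50.

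**Formulas.**
- Paired contrast: noncentral t, df = n − 1, noncentrality dz·√n.
- Four-condition repeated-measures ANOVA: noncentral F, df = 3 and 3(n − 1), noncentrality 4n·f²/(1 − rho), sphericity assumed.

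**Step 1: reproduce the plan's figure.** For 80% power, dz = 0.8 needs n = 15. f = 0.40 needs n = 14 at rho = 0.3 and n = 10 at rho = 0.5. These match the plan's 10–15, so the conventions are a fair reading of it.

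**Step 2: the small effect under the same conventions.** At n = 32, for example, the paired noncentrality is 0.2 × √32 = 1.13. The ANOVA noncentrality at rho = 0.5 is 4 × 32 × 0.01/0.5 = 2.56.

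| n in the analysis | Paired, dz = 0.2 | ANOVA, f = 0.10, rho 0.3 to 0.5 |
|---|---|---|
| 32 (equal split of 64) | 19.5% | 17.3% to 22.9% |
| 50 (all enrolled complete) | 28.4% | 25.6% to 35.0% |
| 64 (pooled, against 7.a) | 35.1% | 32.4% to 44.2% |
| n needed for 80% | 199 | 193 to 138 |

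**Step 3: could a high correlation rescue the claim?** Reaching 80% at f = 0.10 needs rho of about 0.89 at n = 32, 0.82 at n = 50, or 0.77 at n = 64. At those correlations a large effect would need only 4, 5 or 6 people. That is hard to square with the plan's 10–15.

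**Step 4: could repeated time points rescue it?** Section 4.a says "the pain testing battery will be repeated approximately every 90 mins". Suppose 3–5 post-dose time points are averaged (number assumed), the effect is constant over time, and the time points correlate at c = 0.3–0.9. The variance of the averaged difference is then multiplied by (1 + (m − 1)c)/m for m time points. Paired power at dz = 0.2 becomes 21–38% at n = 32 and 30–55% at n = 50. Keeping only c of at least 0.5, where a large effect still needs 10–14 people, the ranges are 21–29% and 30–43%.

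**Step 5: what the sample can detect.** At n = 32, paired power is 99% for dz = 0.8 and 78% for dz = 0.5. The difference detectable with 80% power is dz = 0.51 at n = 32 and 0.40 at n = 50. For one Tukey-adjusted pair among four conditions (critical values 2.616 and 2.599, df = 3(n − 1)), it is 0.61 and 0.49. For pharmacokinetics, an even split of 30 volunteers would give 15 per Phase and a detectable dz of about 0.78.

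**The case against.** The strongest reply is that other conventions also yield 10–15, so 17–23% is not the full range at n = 32. This is true. ANOVA with rho = 0.2 needs 15 for a large effect and gives 15.6% for a small one. A one-sided paired test (7.c does not state sidedness) needs 12 and gives 29.5%. A difference scaled to the raw SD with correlation 0.7 needs 10 and gives 29.3%. Across all matching variants the range is about 16–30%, still far below 80%.

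The plan also says that 10–15 people would suffice, not that they are the minimum, and the figure comes from a cited study whose effect-size metric and correlation the plan does not report. A very high correlation is therefore implausible rather than strictly excluded.

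The figure of 32 per Phase is inferred. The conclusion does not depend on it, because 50 and 64 fail as well. Reading 64 as a per-Phase number would require 128 completers from 100 enrolled.

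Reassurance about medium effects needs a limit. The 78% at dz = 0.5 is for an unadjusted pair; with the planned Tukey adjustment it is about 59% at n = 32.

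Finally, this is an early laboratory study and no decision rule in the plan turns on small-effect power. That limits the harm but does not make the statement correct.

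**Conclusion.** The concern holds: the small-effect claim in 7.c is wrong as written. With about 32 completers per Phase, two-sided power for a conventional small effect is about 17–23%, so such an effect would be missed about 77–83% of the time, against the 20% implied by power 0.8. Other conventions that match the plan's 10–15 widen the power range to about 16–30%. No matching convention reaches 80% at 32, 50 or 64 people. This rests on Cohen's benchmarks and on an equal split of completers, since the plan gives neither an effect size nor completers per Phase.

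The sample is ample for large effects. For medium effects it is close to adequate on unadjusted tests, but less so for Tukey-adjusted pairs. The pharmacokinetic part of the sentence uses the wrong denominator; this is not a demonstrated lack of power.

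**What to change.** In Section 7.c, delete the phrase on small effect sizes. State the expected completers per Phase, the effect-size metric, the correlation assumed and the sidedness. Suitable wording would be: *About 32 completers per Phase give 80% power (two-sided alpha 0.05) for a paired difference of about 0.51 SD of the within-person differences, or about 0.61 SD for a Tukey-adjusted pair; if 50 per Phase complete, about 0.40 and 0.49 SD.*

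Base the pharmacokinetic statement on the roughly 30 blood-draw volunteers and give the number expected per Phase. The 0.78 SD for 15 per Phase is an illustration that assumes an even split, which the plan does not state.

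This changes the text of 7.c only. It adds no participants, procedures or analyses. The one cost is a less favourable stated power.

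### Section 7.c rests its pK sufficiency claim on 64 completers, but pK data come only from a volunteer subset (recruitment aim 30) analysed by Phase, which supports large effects only

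*Combined protocol and SAP*

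**What the plan says.** Section 7.c makes one sample the basis of two claims. It says that "our sample of 64 completers (32/sex) will yield sufficient power" for the CPM and cold pressor outcomes, and the same sentence goes on to say that this sample "will also be sufficient to identify between-session differences on pK results". It gives no effect size, variance or power figure for pK, and it does not mention that only some participants give blood.

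The Study Design Overview in section 4.a does mention it: "A subset of participants will undergo blood draws for pharmacokinetic (pK) profile". Participation in that part is voluntary, and the target is given as an aim: "We will aim to recruit 30 participants that volunteer to undergo IV/blood drawing procedures in order to characterize pK". Section 6 (Pharmacokinetic Analyses) and section 8.b (IV Placement and Blood Draws) also describe a subset.

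Each participant completes one of the two hydromorphone-dose Phases, and "Randomization will be split equally across the two Phases". For Aim 4, section 7.a tests Hyp7 by "evaluating Cmax (maximum concentration) and Tmax (time to maximum concentration) as a function of Drug condition using 1-factor models". The paragraph that follows the aims sets the unit of analysis: "Statistical analyses will be conducted separately by Phase". It makes no exception for pK.

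**The concern.** A participant without blood samples has no Cmax or Tmax and cannot enter the Hyp7 models. On the plan's own target, more than half of the 64 are in that position (64 − 30 = 34). The by-Phase rule then divides the remainder. So the sample credited with being large enough for pK is not the sample that will have pK data, and no other section reconciles the two.

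This matters because Hyp7 is a named hypothesis. Section 6 relies on pK to separate pharmacological enhancement from altered metabolism when the drugs are given together, and says the results will inform which dose combinations go forward. A reader who takes from 7.c that pK was adequately sized on 64 people could give a non-significant Cmax comparison more weight than about 15 people per model can bear.

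**Working it through.** **Inputs from the plan.** 64 completers; alpha 0.05; power 0.80; 10 to 15 people said to be enough for large effects (7.c). Recruitment aim of 30 for blood draws; total n = 100, split equally between Phases (4.a). Separate analysis by Phase (7.a). The 64 must cover both Phases together, because 100 split equally is only 50 per Phase.

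**Assumptions not in the plan.** Two-sided testing. Equal division by Phase of the completers (64 / 2 = 32) and of the blood-draw volunteers (30 / 2 = 15). As an illustration of dropout only, 64/100 applied to 15 gives 9.6, or about 10; no dropout rate is stated.

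**Form of the comparison.** In Tables 1a and 1b each active drug is given in two sessions, once alone and once combined. The pK contrast for each analyte is therefore paired. Let dz be the mean within-person difference divided by the SD of those differences. Power is the probability that a noncentral t variable, with n − 1 degrees of freedom and noncentrality dz × √n, falls outside ± t(0.975, n − 1).

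**The plan's own figure first.** The pK claim cannot be reproduced because it has no effect size or variance. The 10 to 15 figure can be matched if a large effect is taken as dz of 0.8 to 1.0: the required n is 15 at 0.8, 12 at 0.9 and 10 at 1.0.

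**Results.**

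| Participants in the model | Detectable dz, 80% power | Power at dz 0.5 | Power at dz 0.8 |
|---|---|---|---|
| By Phase: 32 (64 halved) | 0.51 | 78% | 99% |
| By Phase: 15 (30 halved) | 0.78 | 44% | 82% |
| By Phase: 10 (after illustrative dropout) | 1.00 | 29% | 62% |
| Pooled: 64 | 0.36 | 98% | >99% |
| Pooled: 30 | 0.53 | 75% | 99% |

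Like for like, the subset raises the detectable difference by a factor of 0.778 / 0.511 = 1.5 by Phase, and by 0.529 / 0.356 = 1.5 if pooled.

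**As a Cmax ratio.** The detectable ratio is exp(dz × √(2 × ln(1 + CV²))). With an assumed within-subject CV of 30% to 60%:

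- 32 per Phase: 1.24 to 1.49
- 15 per Phase: 1.38 to 1.84
- 10 per Phase: 1.51 to 2.18

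For example, at CV 30% the square root is 0.415, so 15 per Phase gives exp(0.778 × 0.415) = 1.38.

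**The case against.** The best defence is that 7.c promises little for pK. It gives no numerical power, and its reference to small effect sizes belongs to CPM and cold pressor. By the plan's own benchmark, about 15 people are enough for a large effect, and the calculation agrees (82% at dz 0.8). On that reading, calling pK sufficient is not false. This stands as far as it goes: the sufficiency of 15 for large effects is not in dispute. It does not rescue the sentence, which credits 64 people and leaves the size of effect unstated.

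A reader might infer that pK power collapses from 98% to 44% at dz 0.5. The documents do not support that contrast. It divides the blood-draw subset by Phase but leaves the 64 whole. The by-Phase rule applies to every analysis, so the comparison is 78% against 44%, or 98% against 75% if pooled.

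A reader might also infer that the sponsor will treat a non-significant Cmax as proof of no interaction. The plan does not say so. Hyp7 predicts an altered profile, and section 7.a also plans Tmax, time-course and pK/pD regression analyses. The risk is one of interpretation, not a stated decision rule.

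Finally, dronabinol is 10 mg in both Phases, so dronabinol-alone data could be pooled. The by-Phase rule as written does not provide for it.

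**Conclusion.** The concern holds as an inconsistency about which sample supports the pK claim. Section 7.c names 64 completers; the design provides a volunteer subset with an aim of 30, analysed by Phase. At about 15 per Phase, pK comparisons have 80% power only for within-person differences of about 0.8 SD, and at about 10 completers per Phase only for about 1.0 SD. For a moderate difference (0.5) power is 44% or 29%, against the 78% that 32 per Phase would give.

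The mismatch between 64 and 30 is certain from the text. The sizes are conditional: they assume a two-sided paired test and an even split of volunteers, and the figure of 10 is illustrative. A 20/10 split would put one Phase at 10 even without dropout. The plan to repeat all analyses with sex as a factor (7.b) would thin the pK models further.

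This should be fixed, but it does not undermine the trial. It does not show that pK is uninformative, or that a stated power figure is wrong, since none is given.

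**What to change.** In section 7.c, remove pK from the sentence about 64 completers and add a separate statement along these lines:

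> Comparisons of pK use the blood-draw subset (recruitment target 30; about 15 per Phase if evenly split, fewer after dropout). Analysed by Phase, this gives 80% power only for standardised within-person differences of about 0.8 with 15 completers per Phase, rising to about 1.0 with 10.

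In section 7.a, under Aim 4, report the Hyp7 Cmax comparison for each analyte as a combination/alone ratio with a confidence interval, so that a non-significant result shows what size of change remains possible and is not read as no interaction.

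The cost is wording and a less favourable stated pK sensitivity. No participants, samples or procedures are added.
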